3.1. Analysis Sets

Analysis sets define the participants to be included in an analysis. Analysis sets and their definitions are provided in this section. The analysis set will be identified and included as a subtitle of each table, figure, and listing.

For each analysis set, the number and percentage of participants eligible for inclusion will be summarized by treatment group and total.

A listing of reasons for exclusion from analysis sets will be provided by participant.

3.1.1. All Randomized Analysis Set

The All Randomized Analysis Set includes all participants who were randomized into the study. This is the primary analysis set for by-participant listings.

3.1.2. Full Analysis Set

The Full Analysis Set (FAS) includes all randomized participants who have received at least one dose of the complete long acting study drug regimen (ie, SC LEN + GS-5423 and GS-2872), and do not have major protocol violation (defined as meeting exclusion criterion of having chronic hepatitis B virus (HBV) infection). This is the primary analysis set for efficacy analyses.

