8.3.1.2. Efficacy

The primary analysis set for efficacy analysis is defined as the Full Analysis Set, which will include all randomized participants who have received at least one dose of the complete long acting study drug regimen (ie, SC LEN + GS-5423 and GS-2872).

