8.10. Sample Size

Although the sample size in this study is determined based on practical considerations and past experience with similar types of studies, assuming the 2 treatment groups have a similar virologic suppression rate, a total of 20 participants in the Primary Cohort will provide at least 35% power to show the lower bound of 95% CI for Week 26 virologic response rate (HIV-1 RNA < 50 copies/mL as defined by the FDA-defined snapshot algorithm) is greater than 83%. It was assumed that the virologic response rate at Week 26 was 95% (based on Gilead studies GS-US-380-1844 and GS-US-380-4030), 12% was a clinically tolerable margin for Phase 1b studies, and a one-sided exact test with a significance level 0.025 was used. The sample size and power calculations were made using the statistical software package PASS (Version 14, NCSS, LLC; Kaysville, Utah, USA).

The estimated 95% CI for possible range of VF rate is provided in [Table 8-1](#). For example, with 1 VF event occurrence (5% estimated VF rate), a sample size of 20 participants can provide 95% confidence that the true VF rate is unlikely to be higher than 24.9%.

Table 8-1. Estimated Virologic Failure Rate and its 95% CIs (from the Clopper-Pearson Exact CI) Based on Number of Virologic Failure Event in Each Group or in Total

Sample Size	20				
Number of VF Events	0	1	2	3	4
Estimate of Incidence of VF (%)	0.0	5.0	10.0	15.0	20.0
Lower Bound of 95% CI (%)	0.0	0.1	1.2	3.2	5.7
Upper Bound of 95% CI (%)	16.8	24.9	31.7	37.9	43.7

VF = virologic failure

Software: SAS® Version 9.4. (SAS Institute Inc., Cary, NC, USA)

A total of approximately 20 participants in the Primary Cohort will provide reasonable assessment of safety and the descriptive PK profile throughout the study. A total of up to 20 participants in the optional Pilot Cohort is based on practical considerations.

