2.2. Primary Analysis

The unblinded primary analysis was conducted after all participants in the Primary Cohort had completed Week 26 visit or prematurely discontinued from the study.

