6.3. Changes from Protocol-Specified Efficacy Analyses

The definition of Full Analysis Set (FAS) is defined differently from the Protocol. Exclusion of participants who have major protocol violation (defined as meeting exclusion criterion of having chronic hepatitis B virus [HBV] infection) from the Full Analysis Set has been added in the SAP.

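### The SAP removes chronic-HBV violators from the Full Analysis Set without giving a reason, and plans no efficacy table on the protocol-defined set

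*SAP*

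**What the plan says.** Protocol 8.3.1.2 defines the primary efficacy set as "all randomized participants who have received at least one dose of the complete long acting study drug regimen". It has no eligibility condition. SAP 3.1.2 keeps that definition and adds that participants "do not have major protocol violation (defined as meeting exclusion criterion of having chronic hepatitis B virus (HBV) infection".

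SAP 6.3 discloses the difference: "The definition of Full Analysis Set (FAS) is defined differently from the Protocol". It names the HBV exclusion but gives neither a reason nor a date.

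The SAP covers the final analysis of both cohorts (SAP 2.4). On the earlier look it reports: "The unblinded primary analysis was conducted after all participants in the Primary Cohort had completed Week 26 visit", or had discontinued (SAP 2.2). SAP 2.1.1 likewise describes the unblinded Week 12 committee review in the past tense.

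SAP 3.1.3 builds the Per Protocol set by removing further participants from the FAS. Two of its removal rules are also protocol exclusion criteria: prior anti-HIV-1 antibodies, and recent or anticipated immunosuppressive or chemotherapeutic treatment.

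**The concern.** Three features together make this worth raising.

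- **The exclusion is selective.** Protocol 4.2 and 4.3 list many criteria, and SAP 4.3 provides for reporting enrolled participants who failed any of them. Only chronic HBV removes someone from the FAS. Prior receipt of an anti-HIV-1 antibody, in a study of such antibodies, removes a participant only from the Per Protocol set. The SAP does not explain the difference.
- **The timing is undocumented.** The text containing the rule postdates unblinded Week 26 results. Nothing available shows that the rule was fixed before those results were seen.
- **Nothing recovers the protocol population.** If anyone is excluded, the efficacy tables will not show the result on the set that the protocol promised.

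At stake is the Week 26 snapshot estimate. With groups this small, one participant can move it visibly.

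**Working it through.** **1. Which set each planned efficacy table uses**

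- Snapshot, both response categories (SAP 6.1.3.1 and 6.1.3.2): FAS, with a supportive analysis on Per Protocol.
- CD4+ count (6.1.3.3): FAS.
- Missing = Failure and Missing = Excluded (6.2.2.1): FAS.
- CD4 percentage, CD8 count and CD4/CD8 ratio (6.2.2.2): FAS.

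Per Protocol is a subset of the FAS, so no table uses the protocol-defined FAS. SAP section 3 describes the long-acting period data in terms of everyone given the complete regimen, but section 6 then names the FAS for each table and takes the snapshot endpoints out of the period analyses.

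**2. Inputs (Protocol 8.10)**

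- Sample size and power: "a total of 20 participants in the Primary Cohort will provide at least 35% power to show the lower bound of 95% CI" above 83%.
- Assumed rate: "It was assumed that the virologic response rate at Week 26 was 95"%.
- Margin: "12% was a clinically tolerable margin for Phase 1b studies", so the reference is 95 − 12 = 83%.
- Test: "a one-sided exact test with a significance level 0.025 was used".
- Interval: Clopper-Pearson, from SAP Appendix 5. With x responders of n, the lower limit is the 0.025 quantile of Beta(x, n − x + 1) and the upper limit is the 0.975 quantile of Beta(x + 1, n − x). For x = n the lower limit is 0.025^(1/n).

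**3. The plan's own figure**

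At n = 20 only 20/20 puts the lower limit above 83%: 0.025^(1/20) = 83.16%. Exact one-sided alpha is 0.83^20 = 0.0241. Power is 0.95^20 = 0.3585, which agrees with the stated minimum of 35%. All five columns of Protocol Table 8-1 also reproduce, for example 1/20: 0.1% to 24.9%.

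**4. Effect of excluding one participant**

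The realised n, the number excluded and their outcomes are not in the documents. The planned 20, about 10 per group, and a single exclusion are assumptions.

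| Participant excluded | Protocol FAS | SAP FAS |
|---|---|---|
| The only non-responder | 19/20 = 95.0% (75.1 to 99.9) | 19/19 = 100% (82.4 to 100) |
| A responder, all respond | 20/20 = 100% (83.2 to 100) | 19/19 = 100% (82.4 to 100) |
| A responder, one non-responder remains | 19/20 = 95.0% (75.1 to 99.9) | 18/19 = 94.7% (74.0 to 99.9) |
| The only non-responder in a group of 10 | 9/10 = 90.0% (55.5 to 99.7) | 9/9 = 100% (66.4 to 100) |

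If the excluded non-responder had HIV-1 RNA ≥ 50 copies/mL, that proportion goes from 1/20 = 5.0% (0.1 to 24.9) to 0/19 = 0% (0 to 17.6).

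The estimate therefore moves by 5.0 points overall, or 10.0 points within a group, when the person removed is the only non-responder. It moves by 0.3 points or not at all in the two responder cases.

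**The case against.** The defence has real substance. Chronic HBV is defined by serology at the screening visit (Protocol 4.3), so it is objective, precedes dosing and cannot be affected by treatment. The change is openly declared. SAP 3.1 promises counts for each analysis set and a listing of reasons for exclusion by participant; SAP 4.3 lists eligibility violators; listings cover all randomized participants; and snapshot outcomes are flagged in them (6.1.2). With so few participants, a reader holding the listings could rebuild the protocol-FAS result. Efficacy is secondary: the primary endpoint is treatment-emergent SAEs through Week 26, and the safety sets carry no HBV exclusion.

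All of that stands, and it limits the weight of the point. It does not remove it. An objective criterion does not explain why that criterion alone was chosen, and a listing is not a tabulated estimate with an interval.

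A reader might go further and infer two things that the documents do not support.

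- **That the exclusion was chosen after seeing the results.** The SAP text postdates the unblinded analysis, but no plan for that analysis is available, the signature dates are redacted and the revision table is empty. The same rule may already have applied at Week 26.
- **That it turns a failed efficacy target into a success.** The 83% figure appears only in the sample-size text, for the Primary Cohort, and no planned conclusion switches on it. A case in the Pilot Cohort would not touch it, because efficacy is not pooled (SAP 3.2.2). At the planned 20, removing a non-responder leaves the lower bound below 83% either way (75.1%, then 82.4%), while removing a responder from 20/20 takes it from above to below. A move from below to above needs, for example, 21 participants: 20/21 (lower bound 76.2%) becoming 20/20 (83.2%). Enrolment of approximately 20 allows that, but nothing shows it happened.

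**Conclusion.** The point holds as a reporting gap. The SAP narrows the protocol's FAS by one selected eligibility violation, gives no reason, does not establish when the rule was set, and leaves no efficacy table on the protocol-defined population. Under the assumptions of 20 participants and one exclusion, the overall secondary snapshot estimate can shift by up to 5.0 points, with a corresponding change in its interval. No direction of bias is shown, and if nobody met the criterion the two sets coincide. The arithmetic supports showing both results; it does not support a claim that the analysis set was tailored to the data.

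**What to change.** - **SAP 6.1.3:** add the Week 26 snapshot results, both < 50 and ≥ 50 copies/mL, on the protocol-defined FAS beside the SAP's FAS. These are the same participants as the Safety Analysis Set for LA Regimen in SAP 3.1.4, which is already being derived. Group them as randomized, because SAP 3.2 would otherwise group that set by treatment received.
- **SAP 6.3:** state why the HBV exclusion was made and when it was decided relative to unblinding.

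The cost is some SAP wording and one extra column, with no new data. The figure on the protocol-defined set may be higher or lower than on the SAP's set. Making the protocol FAS primary again, with HBV moved to the Per Protocol exclusions, is a defensible alternative, but it goes further than the gap requires.

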3.1.3. Per Protocol Analysis Set

The **Per Protocol (PP) Analysis Set** includes all participants in the FAS excluding participants meeting any of the following criteria:

- Did not have on-treatment HIV-1 RNA in the Week 26 analysis window, except when missing is due to discontinuation of study drug for lack of efficacy as in [Table 3-1](#). (Note: lack of efficacy is defined as having the check-box for Lack of Efficacy marked as the reason for premature study drug discontinuation on the study drug completion eCRF page.)
- Received partial or missed doses on Day 1 or Day 2.
- Prior receipt of any anti-HIV-1 mAbs (including ibalizumab).
- Have been treated with immunosuppressant therapies or chemotherapeutic agents (eg, corticosteroids, immunoglobulins, and other immune- or cytokine-based therapies) within 4 weeks of study screening or have an anticipated need for such treatment during the study.

Table 3-1. Participants Excluded from Per Protocol Analysis Set Due to Premature Discontinuation of Study Drug and/or Missing HIV-1 RNA Assessment in Week 26 Analysis Window

Discontinuation from Study Drug prior to or on the Upper Bound of Week 26 Analysis Window		HIV-1 RNA Data on Treatment Available in Week 26 Analysis Window	
		Yes	No
Yes	Due to Lack of Efficacy	+	+
	Due to Other Reasons	+	-
No		+	-

+ = Inclusion of Participants in Week 26 PP analysis set; - = Exclusion of Participants in Week 26 PP analysis set.
On-Treatment HIV-1 RNA data include all HIV-1 RNA data collected up to the earliest date of (196 days [28 weeks] after the dose date of complete long acting regimen, date of restarting ART).

The date of study drug premature discontinuation is the last exposure date for participants who prematurely discontinued study drug.

For the Per Protocol analysis, efficacy data up to the earliest date of (196 days [28 weeks] after the dose date of complete long acting regimen, date of restarting ART) will be included.

The Per Protocol Analysis Set is the secondary analysis set for efficacy analysis.

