6.8. Management of Virologic Rebound and Virologic Failure

Virologic failure is defined as having a rebound of HIV-1 RNA ≥ 200 copies/mL at 2 consecutive visits on or before Week 26, at Week 26, or at study drug discontinuation. Participants who meet criteria for VF will have samples sent for genotypic and phenotypic testing, will restart their baseline ARV regimen (or compatible regimen selected by the investigator), and will continue study follow-up but will not receive additional doses of the study regimen.

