3.8.1. Definition of Key Dates and Study Day

Study Day 1 is defined as the day when the first dose of any study drug was taken, as recorded on the Study Drug Administration eCRF (ie, oral LEN, SC LEN or infusion drugs [GS-5423, GS-2872]).

Last Dose Date is defined as the latest dose date of any study drug as recorded on the Study Drug Administration eCRF (ie, oral LEN, SC LEN or infusion drugs (GS-5423, GS-2872) for participants who prematurely discontinued study drug or completed study drug according to Study Drug Completion eCRF.

Study Days are calculated relative to Study Day 1 of study drug and derived as follows:

- For postdose study days: Assessment Date – First Dose Date + 1
- For days prior to the first dose: Assessment Date – First Dose Date

Baseline Value is defined as the last value obtained on or prior to the first dose of study drug.

Last Study Date is the latest clinic visit dates, and/or the laboratory visit dates, whichever is latest, including the any follow-up visit dates, for participants who prematurely discontinued study or completed study according to the Study Completion eCRF.

Last Exposure Date is defined as follows for participants who prematurely discontinued study or complete study according to Study Completion eCRF (i.e. participant answered “No” or “Yes” for “Did the participant complete the protocol-planned duration of the study” on Study Completion form):

- For participants who receive any injection or infusion, last exposure date is defined as last study date.
- For participants who do not receive any injection or infusion (i.e. for those who only receive oral LEN), last exposure date is defined as the earliest of the last dose date plus 60 days and the last study date.

The last exposure date is defined considering the prolonged exposure of LEN, GS-5423, and GS-2872 after the last dose date of LEN, GS-5423, and GS-2872 through the end of study.

Last Exposure Date of LA Regimen is defined as follows for participants who prematurely discontinued study drug or complete study drug according to Study Drug Completion eCRF (i.e. participant answered “No” or “Yes” for “Did participant complete study drug dosing as specified per protocol” on Study Drug Completion form):

- the earliest date of last study day or ART restart day for participants who prematurely discontinued study or complete study, or

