Appendix 2. Flowchart of US FDA-defined Snapshot Algorithm (for Long Acting Switch Trial)

The following flowchart for US FDA-defined snapshot algorithm is based on the US FDA Guidance on Human Immunodeficiency Virus-1 Infection: Developing Antiretroviral Drugs for treatment {U. S. Department of Health and Human Services 2015}.

*On-Treatment HIV-1 RNA data include all HIV-1 RNA data collected up to the earliest date of (196 days [28 weeks] after the dose date of complete long acting regimen, date of restarting ART).

The dose date of complete long acting regimen refers to the date of dosing with complete long acting drugs (GS-5423, GS-2872, and SC LEN) (ie, Day 1).

Participants with study drug premature discontinuation are defined as participants who were answered “No” to “Did subject complete study drug dosing as specified per protocol?” and had a discontinuation reason other than “Investigator Discretion” (with comment of “Due to Clinical hold”) in Study Drug Completion eCRF).

The date of study drug premature discontinuation is the last exposure date of LA regimen for participants who prematurely discontinued study drug.

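### The note under SAP Table 3-1 dates study drug discontinuation at the last study date, not at ART restart, and so conflicts with the lack-of-efficacy exemption in the same section

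*SAP*

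**What the plan says.** SAP 3.1.3 removes from the Per Protocol set anyone without on-treatment HIV-1 RNA in the Week 26 window, "except when missing is due to discontinuation of study drug for lack of efficacy". The exemption rests on a case report form entry and carries no date: "lack of efficacy is defined as having the check-box for Lack of Efficacy marked as the reason for premature study drug discontinuation". The bullet points to Table 3-1, whose rows are split by this question: "Discontinuation from Study Drug prior to or on the Upper Bound of Week 26 Analysis Window". By Table 3-2 that upper bound is Day 224. Where on-treatment data are lacking, the table keeps the lack-of-efficacy row and excludes the other-reasons row and the No row. The note beneath it fixes the date: "The date of study drug premature discontinuation is the last exposure date for participants who prematurely discontinued study drug".

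SAP 3.8.1 defines two different dates. For the last exposure date: "For participants who receive any injection or infusion, last exposure date is defined as last study date". For the last exposure date of the LA regimen: "the earliest date of last study day or ART restart day for participants who prematurely discontinued study or complete study". The matching note in SAP Appendix 2 uses the second of these: "The date of study drug premature discontinuation is the last exposure date of LA regimen for participants who prematurely discontinued study drug".

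Under protocol 6.8, a participant with virologic failure restarts ART and "will continue study follow-up but will not receive additional doses of the study regimen".

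**The concern.** Every member of the Full Analysis Set received SC LEN and both infusions (SAP 3.1.2), so for everyone who could be in the Per Protocol set the last exposure date is the last study date. A failure who restarts ART early and stays in follow-up as the protocol asks then has a discontinuation date long after Day 224. Table 3-1 treats that participant as not having discontinued in time, and the missing Week 26 value leads to exclusion. The bullet just above the table says that such a participant stays.

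What is at stake is the direction of the supportive analysis. The rule can remove only failures, so the Per Protocol result could look better than the Full Analysis Set result because of a wording slip. The rule applies equally to the Pilot Cohort, which SAP 3.2.2 reports separately.

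**Working it through.** **1. The plan's own figures.** The date rule has no figure of its own. The nearby figures reproduce. For 20/20 the exact lower bound is 0.025^(1/20) = 83.2%, above 83%; for 19/20 it is 75.1%, below it. So 20/20 is needed, and the power at a true rate of 95% is 0.95^20 = 35.8%, in line with the stated 35%. The Clopper-Pearson limits for 0 to 4 failures in 20 match Table 1-1, for example 0.1% to 24.9% for one failure.

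**2. When the situation arises.** On-treatment RNA ends at the earlier of ART restart and 196 days after dosing (SAP 3.1.3, 6.1.2). The Week 26 window is Day 176 to 224. Restart before Day 176 therefore leaves no on-treatment value in the window. Protocol 6.8.1 asks for a retest 2 to 3 weeks after a value of 200 copies/mL or more, that is, nominal day + 14 to nominal day + 21:

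| First elevation | Nominal day | Retest day |
|---|---|---|
| Week 4 | 28 | 42–49 |
| Week 8 | 56 | 70–77 |
| Week 12 | 84 | 98–105 |
| Week 16 | 112 | 126–133 |
| Week 20 | 140 | 154–161 (164 with the +3-day visit window) |
| Week 24 | 168 | 182–189 (179 at the earliest with the −3-day visit window) |

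Weeks 4 to 16 leave ample time for restart before Day 176. Week 20 leaves 176 − 164 = 12 days at the tightest, and the documents give no turnaround time for the confirmatory result, so it counts only if ART is in fact restarted before Day 176. A Week 24 elevation is retested inside the window, so on-treatment data exist and the participant is kept.

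**3. Classification under each date.** Take a failure with the Lack of Efficacy box marked. The two dates were applied for ART restart on Days 60, 118, 160 and 175, with last study dates from the restart day to Day 364. The result was the same for all four restart days:

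| Last study date | Table 3-1 note as written | Date used in Appendix 2 |
|---|---|---|
| Day 224 or earlier | Yes row, lack of efficacy: kept | kept |
| Day 225 or later (e.g. Week 38, Day 266; Week 52, Day 364) | No row, no data: excluded | Yes row, lack of efficacy: kept |

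Leaving the scheduled visits need not bring the last study date forward. Protocol 6.5 then requires follow-up visits at 30, 90 and 180 days after early termination, and SAP 3.8.1 counts follow-up visits. Early termination on Day 160 gives a 90-day visit at about Day 160 + 90 = Day 250.

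**4. Size.** Assume that all other participants are below 50 copies/mL and in the Per Protocol set. Intervals are Clopper-Pearson 95%; when all n respond, the lower limit is 0.025^(1/n).

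| Case | Appendix 2 date | Note as written |
|---|---|---|
| 1 failure of 20, < 50 copies/mL | 19/20 = 95.0% (75.1–99.9) | 19/19 = 100% (82.4–100) |
| 1 failure of 20, ≥ 50 copies/mL | 1/20 = 5.0% (0.1–24.9) | 0/19 = 0% (0–17.6) |
| 1 failure in a dose group of 10, < 50 copies/mL | 9/10 = 90.0% (55.5–99.7) | 9/9 = 100% (66.4–100) |
| 2 failures of 20, < 50 copies/mL | 18/20 = 90.0% (68.3–98.8) | 18/18 = 100% (81.5–100) |

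**The case against.** The best reply is that the intended meaning is clear. The exclusion criterion is the bullet, and it exempts these participants by check-box, with no date. The note is limited to premature discontinuation of study drug, which matches the population of the LA-regimen date; the general last exposure date is defined for those who discontinued or completed the study. The sentences on either side of the note both stop at ART restart. SAP 4.2.1 names the LA-regimen date and then shortens it in the duration formula, so the SAP does use the short form loosely. SAP 6.1.3.1 settles Per Protocol exclusions before database lock, and SAP 3.1 lists the reasons for exclusion, so a wrongly excluded failure would be visible.

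Most of this stands. It shows that Appendix 2 probably carries the intended rule, and that exclusion is one side of a textual conflict, not a settled outcome. It does not remove the conflict: the bullet refers to Table 3-1 for its operation, which brings the reader back to the note, and the two terms are separately defined. A programmer following the definitions would exclude the participant.

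A reader might go further and infer that the Full Analysis Set snapshot is also exposed, because dosing ends on Day 2 while SAP 4.1 and Appendix 2 identify discontinuation by a question on completion of dosing. The documents do not support that. They do not show how sites answered; protocol 6.6 lists virologic failure as a reason to discontinue, SAP 1.2.4 puts treatment at about 26 weeks, and the study drug completion form has a Lack of Efficacy box.

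**Conclusion.** The conflict is real, and the point is minor. Under the note as written, a failure is dropped from the Per Protocol set when three things hold together: Lack of Efficacy is marked, ART is restarted before Day 176, and the last study date is after Day 224. That covers first elevations at Weeks 4 to 16, and at Week 20 if restart comes before Day 176.

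Only the supportive Per Protocol analysis changes. The Full Analysis Set snapshot uses the Appendix 2 date and counts the same participant as 50 copies/mL or more. The primary endpoint and the power statement are untouched. Nor is there a false pass of the 83% benchmark, which a reader might suspect from a 100% result: the lower limits of 82.4% and 81.5% remain below it. The percentages are illustrations, since the documents give no failure counts; with no such failure, nothing changes.

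**What to change.** In the note under Table 3-1, replace *last exposure date* with *last exposure date of LA regimen*, as in Appendix 2. The table, the bullet and the snapshot algorithm then agree. The cost is three words: SAP 3.8.1 already defines the date, and no new data or derivation is needed. The change should be made before the Per Protocol exclusions are settled at database lock.

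No wider rule that ART restart always counts as discontinuation is proposed. It would override the clinical-hold exception in SAP 4.1 and Appendix 2, and would alter disposition and snapshot rules after the unblinded Week 26 primary analysis, which SAP 2.2 reports as already done.
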